#### 5.4 Participant Withdrawal

Study participants will be withdrawn from the study if found to have been initially ineligible or incapable of following through with mupirocin or chlorhexidine treatment regimen. Study participants will be withdrawn if all of their specimens from visit 1 are negative for *S. aureus* by microbiological culture. These participants will be contacted by phone. No further follow-up with withdrawn participants is required.

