#### 5.5 Medication

All medications are permitted during the study period. It is possible that some study participants will take antibiotics for clinical reasons during their time in the study. They will continue to be followed throughout the study as a 'natural' experiment, but their post-antibiotic data will be excluded from the primary analysis.

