#### 11.3 Sample Size Estimates

How many participants (or specimens, or charts) will be used in this study? Local: 250 Worldwide: 250

We plan on enrolling 250 participants to end up with a final sample size of 40. We assume that approximately one in five participants will have *S. aureus* colonization at the screening/enrollment visit. We assume that 10 participants will become ineligible during the course of the protocol because of hospitalization or antibiotic administration. The final sample

size was chosen based on feasibility and cost. Unlike more traditional genetic association studies, where theoretical sample calculations can be performed, the current study uses more novel data mining approaches applied to data obtained from high-throughput genotyping technology, in which many different potential OTUs are compared between groups (pre and post decolonization within a participant). Currently, there is no generally accepted theoretical power calculations for the analyses proposed here. Since the participants will serve as their own controls (pre and post decolonization), we increase power to detect significant differences and potentially avoiding confounding factors (27).

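### Section 5.4 can remove treated participants from follow-up for not completing the regimen, and Section 11.3 counts antibiotic users as ineligible although Section 5.5 keeps them in the study

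*Protocol*

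**What the plan says.** Two sets of statements in the protocol bear on who is followed and analysed after treatment.

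**Not completing the regimen.** Section 5.4 withdraws participants who were ineligible at entry or are "incapable of following through with mupirocin or chlorhexidine treatment regimen". It adds: "No further follow-up with withdrawn participants is required". Section 7.3 says that if a product is not tolerated, that product is stopped; it does not mention withdrawal. Section 7.5 has participants log missed doses and call if two or more are missed. It lets the investigator supply two more doses and has the log reviewed at Week 9. It does not mention withdrawal either.

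**Antibiotics and hospitalization.** Section 5.5 says of participants who take antibiotics: "They will continue to be followed throughout the study as a 'natural' experiment", and "their post-antibiotic data will be excluded from the primary analysis". Section 11.3 says: "We assume that 10 participants will become ineligible during the course of the protocol because of hospitalization or antibiotic administration". Section 5.4 lists neither event as a reason for withdrawal. Section 5.3 excludes recent or planned hospitalization at entry, but no section says what happens to the data of someone admitted during the study.

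Section 11.2 is where this matters most. It sets out to describe how well the regimen reduces MRSA, MSSA and Gram-negative colonization, to compare acquisition of Gram-negative bacilli between community and nursing-home participants, and to compare time to recolonization.

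**The concern.** A participant who starts the regimen and cannot finish it is informative. That person may not have cleared *S. aureus*, may have reacted to a product, or may have acquired Gram-negative organisms. If Section 5.4 is applied after product is dispensed, whether the person stays under observation depends on what happened on treatment. The before-and-after comparison is then made in a group selected after exposure. No statistical analysis plan can repair this, because specimens never collected cannot be analysed.

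The phrase in Section 5.4 is also undefined. Someone who stops one product under Section 7.3, or misses doses under Section 7.5, might be kept at one investigator's discretion and withdrawn at another's.

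The antibiotic and hospitalization rules raise a related problem. Sections 2.2 and 2.3 ask whether decolonization promotes Gram-negative colonization and note that this might raise infection risk. An infection can lead to antibiotics or admission, so losing people for those events can be connected with the harm under study. Sections 5.5 and 11.3 give different accounts of whether such people are lost at all.

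**Working it through.** **1. The plan's own figure.** Inputs from Section 11.3: "We plan on enrolling 250 participants to end up with a final sample size of 40"; "We assume that approximately one in five participants" will be colonized at screening; 10 are later lost to hospitalization or antibiotics.

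- Colonized: 250 × 1/5 = 50.
- Final: 50 − 10 = 40, which reproduces the stated 40 exactly.
- Planned loss: 10/50 = 20% of the colonized group.

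The 40 is reached only by subtracting all 10 as ineligible. The arithmetic contains no allowance for withdrawals under Section 5.4.

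**2. When the Section 5.4 rule can act.** Section 8.1 collects specimens at Day 0, Week 4 and Week 8, and dispenses product at Week 8. The later occasions are Weeks 9, 10, 11, 12 and 16 and Month 12. Three of the nine occasions therefore precede product and six follow it. A participant withdrawn during the five-day course could lose all six.

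**3. Sections side by side.**

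| Event | One section | Another section |
|---|---|---|
| Product not tolerated | 7.3: that product stops; withdrawal not mentioned | 5.4: withdrawn if unable to follow through |
| Missed doses | 7.5: logged, may be replaced, reviewed at Week 9 | 5.4: withdrawn if unable to follow through |
| Antibiotics | 5.5: followed; later data left out of the primary analysis | 11.3: ineligible, subtracted from the total |
| In-study hospitalization | 5.4: not a withdrawal reason | 11.3: ineligible, subtracted from the total |

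**4. What losing the 10 outright would mean.** Let x be the number with an outcome among the 40. If nothing is known about the other 10, the proportion in all 50 lies between x/50 and (x + 10)/50. The width is 10/50 = 20 points whatever x is. With assumed rates for illustration:

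- Gram-negative acquisition of 10% in the 40: x = 4, so 4/50 = 8% to 14/50 = 28%.
- Clearance of 70% in the 40: x = 28, so 28/50 = 56% to 38/50 = 76%.
- If acquisition is 10% in the 40 and two or three times that in the other 10, the rate in all 50 is (4 + 2)/50 = 12% or (4 + 3)/50 = 14%.

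These are limits and illustrations under the Section 11.3 wording, not estimates of bias. Under Section 5.5 some of the 10 would contribute post-treatment specimens before their first antibiotic, and the range would narrow.

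**5. Withdrawals under Section 5.4.** The protocol gives no rate. If 5%, 10% or 20% of the 50 were withdrawn for not completing (assumed, and not overlapping with the 10), the final number would be 47.5 − 10 = 37.5, 45 − 10 = 35 or 40 − 10 = 30, against the planned 40.

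**The case against.** The case on the other side is substantial, and several parts of it stand.

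- **A completers-only trial.** A reader might infer that effectiveness and Gram-negative harm are estimated only in healthy people who finished the regimen. The protocol does not support that. Section 5.5 keeps antibiotic users in follow-up and retains their earlier data, and Section 11.2 states no restriction to completers. Sections 7.3 and 7.5 do not tie a stopped product or missed doses to withdrawal, so people with imperfect adherence can be expected at Week 9.
- **The wording of Section 5.4.** It can be read as the counterpart of the Section 5.2 entry criterion on being able to use the products. It also says that follow-up is not required, which neither forbids contact nor discards data already collected. This is fair, but the text does not confine the rule to the period before Week 8.
- **Harm vanishing from the record.** A reader might infer this too. Section 9 provides for detecting and reporting serious events, Section 13 for grading adverse events, and Section 8.1 for a medical history and medication review at visits through Week 16. The gap is limited to people actually withdrawn.
- **The cause of the 10 losses.** Some would occur in the eight weeks before product is dispensed and cannot depend on response to it. Nothing shows that the rest are mainly infections due to the regimen. Leaving out data after systemic antibiotics is defensible in a microbiome study, because antibiotics alter the outcome directly.
- **Recovering all 50.** It is tempting to say that using pre-antibiotic data restores 50 participants and narrows a 95% half-width around 50% from 1.96 × √(0.25/40) = 15.5 points to 1.96 × √(0.25/50) = 13.9. This fails for post-treatment proportions, because anyone given antibiotics before Week 8 has no uncensored post-treatment outcome.
- **Section 11.3 as a planning assumption.** Its 40 may mean participants with full uncensored follow-up, which would fit Section 5.5. If so, the section should say that; its present word is ineligible.
- **Analysis sets belong in a statistical analysis plan.** Often true. The withdrawal rule and the conflict between Sections 5.5 and 11.3 are nonetheless matters for this document.

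**Conclusion.** The concern holds in two limited parts.

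First, Section 5.4 permits withdrawal after exposure for reasons that arise on treatment, requires no follow-up, and is not reconciled with Sections 7.3 and 7.5. The Section 11.2 estimates may therefore lean toward completers. How far, and in which direction, cannot be computed: the protocol gives no rate of non-completion and no outcome rates by completion. Any contrast between success in completers and in all treated participants would rest on invented rates. A difference in antibiotic use between community and nursing-home participants is likewise possible but not documented here, since the companion protocol is not shown.

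Second, Sections 5.5 and 11.3 disagree on participants given antibiotics, and hospitalization during the study has no stated handling. The number affected is the plan's own: 10 of 50, or 20%. The 20-point range applies only if all 10 contribute no outcome, which is what Section 11.3 implies and Section 5.5 does not.

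This should be corrected by amendment. It does not undermine the study as a whole.

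**What to change.** - **Section 5.4:** separate not completing product from leaving the study. Everyone dispensed product at Week 8 stays in the specimen visits already scheduled, unless found to have been ineligible at entry or consent is withdrawn.
- **Sections 5.4, 7.3 and 7.5:** reconcile them, and define what counts as being unable to follow through. No rule on stopping or replacing treatment needs to change for this.
- **Section 11.2:** report the culture outcomes for all participants dispensed product, with completers as a supplementary set.
- **Section 11.3:** match it to Section 5.5. Participants contribute data up to their first antibiotic, and 40 is the number expected to have full uncensored follow-up. State the same handling for hospitalization during the study.
- **Sensitivity analysis:** repeat the culture analyses with the post-antibiotic data included. Section 5.5 already provides for continued follow-up of these participants.

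The cost is amendment wording, a few already scheduled visits for people who did not complete product, and one extra analysis.

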#### 5.5 Medication

All medications are permitted during the study period. It is possible that some study participants will take antibiotics for clinical reasons during their time in the study. They will continue to be followed throughout the study as a 'natural' experiment, but their post-antibiotic data will be excluded from the primary analysis.

### 6 Informed Consent Process for Participants

At the initial visit, the study coordinator will verbally review the written informed consent and HIPAA form with the potential participant in a private area. The potential participant will be asked if he/she wishes for the study coordinator to read the consent form verbatim or to summarize it as he/she follows along.

Because cognitive impairment is possible in the adult population and participants need to be "Capable of understanding and complying with the entire study protocol", each potential participant will be evaluated for his/her ability to give informed consent. The potential participant must be alert and able to communicate in order to give informed consent. He /she will be asked the following questions before informed consent to participate is considered to have occurred: "Why are we doing the study? Does the study have any risks? What are you going to do in the study? Do you have to participate in the study? If you don't want to be in the study anymore, what do you do?" as described in Evaluation to Sign Consent. If the potential participant is unable to answer these questions correctly after two opportunities, he/she will not be eligible.

### 7 Study Intervention

### 7.1 Study Product Description

#### 7.1.1 Acquisition

BACTROBAN NASAL ointment (mupirocin calcium ointment, 2%) and antimicrobial antiseptic skin cleanser (4% chlorhexidine) will be shipped to the VAMHCS Investigational Pharmacy.

#### 7.1.2 Formulation, Packaging, and Labeling

The study products are BACTROBAN NASAL ointment (mupirocin calcium ointment, 2%) and antimicrobial antiseptic skin cleanser (4% chlorhexidine). BACTROBAN NASAL is a licensed medication packaged and labeled by GlaxoSmithKline. BACTROBAN NASAL (mupirocin calcium ointment, 2%) is packaged in 1.0-gram tubes and is for intranasal use only. Antimicrobial antiseptic skin cleanser (4% chlorhexidine) is an FDA-approved medication packaged in 16 oz containers.

### 7.1.3 Product Storage and Stability

BACTROBAN NASAL ointment (mupirocin calcium ointment, 2%) and antimicrobial antiseptic skin cleanser (4% chlorhexidine) will be stored between 20-25°C (68-77°F), as directed by the manufacturers.

### 7.2 Dosage, Preparation and Administration of Study Intervention

Participants will be self-treated with antimicrobial antiseptic skin cleanser (4% chlorhexidine) topically 3 times within 5 days before the Week 9 visit. Participants will also be self-treated with BACTROBAN NASAL ointment (mupirocin calcium ointment, 2%) intranasally in the 5 days before the Week 9 visit.

### 7.3 Modification of Study Intervention

If a participant develops allergic symptoms or other signs of intolerance to antimicrobial antiseptic skin cleanser (4% chlorhexidine) or BACTROBAN NASAL, that medication will be stopped.

### 7.4 Accountability Procedures for the Study Intervention

The PI is responsible for ensuring that a current record of product disposition is maintained and product is dispensed only at an official study site by authorized personnel as required by applicable regulations and guidelines.

Antimicrobial antiseptic skin cleanser (4% chlorhexidine) and BACTROBAN NASAL ointment (mupirocin calcium ointment, 2%) will be distributed to participants by the General Clinical Research Center at the University of Maryland Medical Center. Documentation of all products received, distributed and destroyed will be kept by the research pharmacist. An assigned study monitor will review the pharmacy records for accuracy and completeness.

### 7.5 Assessment of Participant Compliance with Study Intervention

At the Week 8 study visit, three doses of antimicrobial antiseptic skin cleanser (4% chlorhexidine) and ten doses of BACTROBAN NASAL ointment (mupirocin calcium ointment, 2%) will be dispensed to all participants. Instructions regarding dosing, missed doses and possible side effects will be provided. In addition, a Compliance log will be provided for the participant to document the date and time required study doses were taken. In addition, missed doses will be recorded on this log and the participant will be instructed to call the Investigator if two or more doses are missed. The Investigator may decide to provide the participant with an additional two doses.

At the Week 9 study visit, the log will be reviewed to determine compliance with study medication.

# 8 Study Procedures/Evaluations

#### 8.1 Clinical Evaluations

Day 0 (enrollment visit) – Will occur in the GCRC:

- Screen participant regarding inclusion and exclusion criteria.
- Obtain informed consent.
- Obtain demographic information and a brief medical history by interview. The brief medical history includes current and recent medications and past medical and surgical history.
- Collect vital signs and basic anthropometric measurements in order to determine eligibility. Participants deemed eligible for the study will be enrolled at this visit.
- Measure oral temperature to screen out participants with febrile infectious disease.
- Complete a brief physical assessment of the culture sites.
- Obtain a 40 mL blood sample and specimens from the following sites: anterior nares, posterior pharynx, skin over the femoral vein, skin over the subclavian vein, and perirectal skin (see SOP for Methods).
- Counsel participant to refrain from using any antibacterial/antiseptic products for 48 hours before visits.
- Counsel participant to refrain from swimming in a chlorinated pool or using a hot tub in the 48 hours before visits.
- Counsel participant to refrain from bathing or showering in the 12 hours prior to the study visit.
- Inform participant that if specimens are negative for *S. aureus*, he/she will be withdrawn from the study at week 4.

For participants who do NOT meet eligibility criteria to continue in the study: (if MRSA and MSSA negative on all enrollment cultures)

- 1) Inform participant via phone that all enrollment specimens were MRSA and MSSA negative and withdraw him/her from the study.
- 2) Complete Participant Deactivation Form

Week 4 – Will occur in the GCRC:

- Review results of cultures from Day 0 to determine eligibility
- Reconfirm participant's willingness to participate in the study.
- Confirm that participant has abstained for the last 48 hours from the following: using any antibacterial/antiseptic products, swimming in a chlorinated pool or using a hot tub.
- Record time and date of last bath or shower.
- Measure oral temperature to screen out participants with febrile infectious disease.
- Collect a focused medical history.
- Review concomitant medications

- Complete a brief physical assessment of their anterior nares, posterior pharynx and skin sites.
- Obtain specimens from the anterior nares, posterior pharynx, skin over subclavian vein, skin over femoral vein and perirectal skin.
- Counsel participant to refrain from using any antibacterial/antiseptic products for 48 hours before visits.
- Counsel participant to refrain from swimming in a chlorinated pool or using a hot tub in the 48 hours before visits.
- Counsel participant to refrain from bathing or showering in the 12 hours prior to the next study visit.

Week 8 – Will occur in the GCRC:

- Reconfirm participant's willingness to participate in the study.
- Confirm that participant has abstained for the last 48 hours from the following: using any antibacterial/antiseptic products, swimming in a chlorinated pool or using a hot tub.
- Record time and date of last bath or shower.
- Measure oral temperature to screen out participants with febrile infectious disease.
- Collect a focused medical history.
- Review concomitant medications
- Complete a brief physical assessment of their anterior nares, posterior pharynx and skin sites.
- Obtain specimens from the anterior nares, posterior pharynx, skin over subclavian vein, skin over femoral vein and perirectal skin.

For participants who meet eligibility criteria to continue in the study:

- Provide a 16oz of antimicrobial antiseptic skin cleanser (4% chlorhexidine) to participant. Educate participant on how to use the skin cleanser in the shower on all of their skin from the neck down.
- Provide ten doses of mupirocin ointment to participants. Educate participant on how to self-apply the ointment intranasally.
- For each medication, provide instructions regarding application, dosing, missed doses and possible side effects.
- Provide a Compliance Log to participant to document the date and time required study doses are taken. Instruct participant to also record missed doses on the log, and to call the Investigator if two or more doses are missing. The Investigator may decide to provide the participant with an additional two doses.
- Counsel participant to refrain from using any antibacterial/antiseptic products for 48 hours before visits.
- Counsel participant to refrain from swimming in a chlorinated pool or using a hot tub in the 48 hours before visits.
- Counsel participant to refrain from bathing or showering in the 12 hours prior to the next study visit.

Week 9 – Will occur in the GCRC:

- Reconfirm participant's willingness to participate in the study.
- Confirm that participant has abstained for the last 48 hours from the following: using any antibacterial/antiseptic products, swimming in a chlorinated pool or using a hot tub.
- Record time and date of last bath or shower.
- Measure oral temperature to screen out participants with febrile infectious disease.
- Collect a focused medical history.
- Review concomitant medications.
- Complete a brief physical assessment of their anterior nares, posterior pharynx and skin sites.
- Obtain specimens from the anterior nares, posterior pharynx, skin over subclavian vein, skin over femoral vein and perirectal skin.
- Review the Compliance Log to determine compliance with the 5-day course of mupirocin/chlorhexidine.
- Counsel participant to refrain from using any antibacterial/antiseptic products for 48 hours before visits.
- Counsel participant to refrain from swimming in a chlorinated pool or using a hot tub in the 48 hours before visits.
- Counsel participant to refrain from bathing or showering in the 12 hours prior to the next study visit.

Weeks 10, 11, 12, and 16-Will occur in the GCRC:

- Reconfirm participant's willingness to participate in the study.
- Confirm that participant has abstained for the last 48 hours from the following: using any antibacterial/antiseptic products, swimming in a chlorinated pool or using a hot tub.
- Record time and date of last bath or shower.
- Measure oral temperature to screen out participants with febrile infectious disease.
- Collect a focused medical history.
- Review concomitant medications
- Complete a brief physical assessment of their anterior nares, posterior pharynx and skin sites.
- Obtain specimens from the anterior nares, posterior pharynx, skin over subclavian vein, skin over femoral vein and perirectal skin.
- Counsel participant to refrain from using any antibacterial/antiseptic products for 48 hours before visits.
- Counsel participant to refrain from swimming in a chlorinated pool or using a hot tub in the 48 hours before visits.
- Counsel participant to refrain from bathing or showering in the 12 hours prior to the next study visit.

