### 5 Selection and Withdrawal of Participants

### 5.1 Recruitment of Study population

All study participants will be adults that live in Baltimore or the surrounding area. Community dwelling participants will be recruited from the Managed Care Clinics of the Baltimore VA Medical Center (via an IRB approved flier), by conducting a screening of the VA medical records for patients with cultures positive for S. aureus in the last three years in the VA Maryland HCS (via an IRB approved letter mailing), and approved VA research registries (via an IRB approved letter). In addition, we will recruit from students and employees of the University of Maryland Baltimore and the VA Maryland HCS (via an IRB approved flier).

When contacted about participation, the study coordinator will review the information from the study flier or letter with the potential participant and answer questions. If the potential subject is interested in participating, the study coordinator will review the eligibility criteria prior to scheduling the Enrollment Visit in the General Clinical Research Center (GCRC) in order to screen out ineligible participants by history. Identifying information will only be collected on those potential participants who are scheduled for the screening/enrollment visit.

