#### Month 12 (+/- 3 months) Follow-up visit- Will occur in the GCRC

Clinical procedures are completed by GCRC staff. However, in extreme circumstances it is possible for this study visit to be completed at the participant's home, in which case the follow-up visit procedures are completed by a trained research staff member.

- Participants previously enrolled prior to 12 month follow-up visit being added, will need to be re-consented at the 12 month follow-up visit prior to any data/specimen collection.
- Participants who were consented for the 12 month follow-up visit will have the consent form reviewed with them prior to any data/specimen collection.
- 1) Obtain nose culture see Appendix 2 "Method for Obtaining Nose Culture".
- 2) Obtain throat culture see Appendix 3 "Method for Obtaining Throat Culture".
- 3) Obtain skin cultures see Appendix 4 "Method for Obtaining Skin Cultures".
- 4) Interview participant and complete the follow up visit form.

The visit time points represent ideal visit times, but this exact timing is not required. We will be using the following guidelines:

- 1) All follow-up visits through visit 8 must occur no more than 18 weeks after enrollment.
- 2) Participants should have 3 sets of specimens collected in the 2 months prior to administration of chlorhexidine/mupirocin. These initial 3 sets of specimens can occur no closer than 2 weeks apart.
- Participants should have 4 sets of specimens collected in the 4 weeks after chlorhexidine/mupirocin administration. These 4 sets of specimens can occur no closer than 5 days apart.
- 4) Participants should have an 8thset of specimens collected after the 4 weekly sets of specimens. This 8th set of specimens can occur no closer than 2 weeks after the last weekly specimens (which should have been collected at approximately week 12).
- 5) The 12 month follow-up visit should occur between the 9th and the 15th month after the partciapants original date of enrollment in the study.

Specimens not collected at the designated time or missed altogether will not be reported as deviations. Missed visits will not be reported as deviations.

See SOPS for detailed procedures of visit conduct, specimen collection, and case report forms.

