### 11.2 Analysis Plan for Microbiologic Data

The goals of the microbiological analysis are two-fold. The first goal is descriptive to document the effectiveness of the regimen in reducing colonization with MRSA, MSSA and pathogenic Gram-negative bacilli at the body sites sampled. The second goal will compare the effectiveness of the regimen in the two different populations. We will assess whether there are differences in acquisition of GNB and antibiotic resistant GNB between community-dwelling and nursing home-dwelling adults. We will compare weeks to MRSA or MSSA re-colonization in each body site by living environment using survival curves and the Wilcoxon log rank test. We will compare whether there are differences in the acquisition (among those negative at baseline) of specific GNB and resistant GNB between community-dwelling and nursing MRSA or MSSA-colonized adults using chi-square tests or Fisher's exact test as appropriate.

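### Day 0 swabs are taken before participants are told of the antiseptic, pool and bathing restrictions and without the checks used at Weeks 4 to 16, so one of three baseline sets has unrecorded washing exposure

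*Protocol*

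**What the plan says.** **Day 0.** The Day 0 list in Protocol section 8.1 collects blood and swabs from all five sites: "Obtain a 40 mL blood sample and specimens from the following sites: anterior nares, posterior pharynx, skin over the femoral vein", followed by the subclavian and perirectal skin. The restrictions come after that item. The one on antiseptics reads: "Counsel participant to refrain from using any antibacterial/antiseptic products for 48 hours before visits". Pools and hot tubs get the same 48-hour limit in a separate item. The one on washing reads: "Counsel participant to refrain from bathing or showering in the 12 hours prior to the study visit".

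**Weeks 4 to 16.** Each visit list in this period opens with a check that Day 0 lacks: "Confirm that participant has abstained for the last 48 hours from the following: using any antibacterial/antiseptic products", and likewise pools and hot tubs. Each also notes when the participant last bathed or showered.

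**Before Day 0.** Section 5.1 describes one contact, in which the coordinator goes over the flier or letter and "the study coordinator will review the eligibility criteria prior to scheduling the Enrollment Visit". It mentions no preparation for sampling.

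**How Day 0 is used.** Sections 5.2 and 5.4 require at least one positive enrollment culture and withdraw anyone whose visit 1 specimens are all negative. The timing guidelines at the end of section 8.1 add: "Participants should have 3 sets of specimens collected in the 2 months prior to administration of chlorhexidine/mupirocin". On the visit schedule these are Day 0, Week 4 and Week 8.

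**The concern.** The protocol treats recent antiseptic use, pool or hot-tub use and bathing as important enough to counsel on and follow up at seven consecutive visits. It leaves them unmanaged at the first visit, which has two special roles.

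- Day 0 is the only gate for *S. aureus* colonization, and no repeat culture is provided for someone who tests negative.
- Day 0 is one of three pre-treatment sets. Section 11.3 relies on participants being their own controls, so a sampling condition that differs only on the pre-treatment side weakens that comparison.

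Because nothing is recorded, the affected Day 0 samples cannot be identified, adjusted for or set aside at analysis.

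**Working it through.** **1. Visit lists side by side (section 8.1).**

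| Item | Day 0 | Weeks 4, 8, 9, 10, 11, 12, 16 |
|---|---|---|
| Swabs at five sites | yes | yes |
| Restrictions explained at an earlier listed visit | no | yes |
| 48-hour abstention check | no | yes |
| Last bath or shower noted | no | yes |

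Of the 8 visits through Week 16, 7 have both items and Day 0 has neither. (The Month 12 list also omits them, but that visit is neither baseline nor an eligibility visit.) The bathing item at Day 0 refers to the study visit, whereas later lists refer to the next one. Coming after the swabs, it can only govern later visits.

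**2. Share of the baseline.** Three pre-treatment sets are planned and Day 0 is one of them: 1/3 = 33%.

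**3. Effect of a Day 0 shift.** Assume the baseline is a simple mean of the three sets, and that unprepared sampling shifts the Day 0 value by b within-person SDs. The baseline mean then moves by b/3:

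- b = 0.5 gives 0.5/3 = 0.17 SD
- b = 1 gives 1/3 = 0.33 SD

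The documents give neither the size nor the sign of b, so these values show scale only.

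**4. The plan's own sample size.** Section 11.3 enrolls 250, assumes one in five colonized at the screening/enrollment visit, and allows for 10 later losses: 250 × 1/5 = 50; 50 − 10 = 40. This matches the stated final 40. The proposed change alters none of these figures.

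**5. Precision if Day 0 is left out.** Assume equal, independent within-person variance and the four post-treatment sets planned for the four weeks after treatment. The standard error of a pre/post difference, in within-person SDs, is √(1/n_pre + 1/n_post):

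- three pre-treatment sets: √(1/3 + 1/4) = 0.764
- two pre-treatment sets: √(1/2 + 1/4) = 0.866
- ratio: 0.866/0.764 = 1.13, about 13% larger

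This applies when Day 0 is dropped for everyone. Dropping only the sets that fail the check costs less.

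**The case against.** **Unseen material may fill the gap.** The flier, letter and SOPs are not shown, and any of them could carry a preparation instruction or a bath field. This stands as a limit on saying that participants first hear of the restrictions at Day 0. It does not explain why an itemised Day 0 list omits two items that each list from Week 4 to Week 16 spells out.

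**Day 0 is not wholly uncontrolled.** Section 5.3 excludes systemic antibacterials or antifungals and nasal antimicrobial ointment in the past 3 months, and Day 0 includes a temperature and a medication history. This stands. The gap is confined to topical antiseptic, pool or hot-tub, and bathing exposure.

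**Wrongful withdrawal is limited.** One positive site of five is enough, and nares and throat are plausibly the sites least affected by washing. This stands.

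A reader might also draw four stronger conclusions that the documents do not support.

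- *The study will fall short of 40.* No share of carriers missed at Day 0 is given. The one-in-five figure is tied to the enrollment visit, so it may already reflect sampling as performed there; a further deduction could count the same loss twice.
- *The bias runs toward the hypothesised rise in Gram-negative bacilli.* Section 11.1 includes relative as well as absolute abundance, and washing that removes Gram-positive organisms could raise the Gram-negative share at Day 0.
- *Gram-negative acquisition is inflated.* Section 11.2 plans this: "We will compare whether there are differences in the acquisition (among those negative at baseline) of specific GNB and resistant GNB", between community-dwelling and nursing-home adults. Any bias in that contrast depends also on sampling in the companion protocol, which is not shown. If baseline means all three sets, Weeks 4 and 8 would correct many false negatives.
- *Every later sample follows 48 hours without antiseptic.* Section 7.2 places chlorhexidine use within the 5 days before Week 9, and nothing shown fixes the last use 48 hours before the swabs. The Week 9 check and that treatment window need to be reconciled separately.

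**Conclusion.** The point holds in a limited form. Followed as written, the protocol collects one third of the pre-treatment specimen sets, and all the cultures that settle *S. aureus* eligibility, without preparation stated in advance and without a record of topical antiseptic, pool or bathing exposure. The seven later visits through Week 16 are handled differently. This is a weakness in baseline comparability that cannot be repaired after the fact, because the data needed to examine it are not collected.

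No bias estimate can be given. The b/3 scaling rests on a simple three-set mean and an unknown b; the 13% precision cost rests on equal, independent variances and four post-treatment sets. The change is worth making because it is cheap, not because a large error has been shown.

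**What to change.** 1. Add to the Day 0 list, after consent and before the swabs, the same abstention check and record of last bath or shower used from Week 4.
2. Give the 48-hour and 12-hour preparation instructions at the scheduling contact already described in section 5.1. Consent is taken at Day 0 and must precede any study procedure (section 12), so the script needs IRB approval for an instruction given before consent.
3. Prespecify a sensitivity analysis of the pre/post microbiome and Gram-negative comparisons that omits Day 0 sets failing the check and takes Weeks 4 and 8 as baseline.

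Mandatory rescheduling or exclusion from the main analysis is not proposed. No other visit attaches a consequence to a failed check, so that would be stricter than the rule elsewhere in the protocol.

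Cost: two form fields, an IRB-approved script change, and a less precise baseline in the sensitivity analysis, at most the 13% shown above under the same assumptions.
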